## **4. METHODS AND PROCEDURES**

Subjects will be volunteer patients with hypertrophic cardiomyopathy who will be undergoing myectomy from the HCM Program. Before cardiopulmonary bypass the anterior septal thickness at the point of mitral-septal contact will be measured by TEE in 120 degree view. The distance from the aortic annulus of this location will also be noted. With OPIE the PI will measure this thickness at the

site of mitral-septal contact as assessed by the location of the contact lesion (callous) and confirmed by the cm below the aortic annulus. After resection the residual thickness of the septum will be measured both by OPIE and by post-cardiopulmonary bypass TEE. The thickness of the surgical specimen will be measured. The differences between the OPIE and TEE measured septal thicknesses provide the primary data points for the statistical analysis.

We estimate that the cardiopulmonary bypass time of the OPIE will be prolonged 3 minutes. This may be offset by faster myectomy time gained by more confidence of septal thickening. Length of stay should not be prolonged.

We will enroll 10 subjects in this pilot study. Subject participation will be complete after their hospitalization for surgery. No follow-up visits are necessary, outside of the routine post-op care.

In general, results from studies, which use data, collected as part of this research will be preliminary, and the clinical implications of any findings may not be understood for years. Therefore, individual study results will not be disclosed to the patient and/or his or her healthcare provider(s). Data will be stored in a database housed within the Department of Cardiothoracic Surgery. The above mentioned database will be stored until the end of the study in a password protected secure computer server accessible only by the principle investigator, co-investigators and research staff listed for this project.

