## **7. POTENTIAL RISKS TO SUBJECTS**

There are minimal risks to subjects. Although health information that is collected will be kept in a secure server, there is always the risk that it may be accessed by individuals not associated with this study. Efforts will be made to protect confidentiality as outlined in this protocol. We estimate that the cardiopulmonary bypass time of the OPIE will be prolonged by 3 minutes. This may be offset by faster myectomy time gained by more confidence of septal thickening. This potential increased confidence in performing the myectomy by knowing the thickness of the septum highlights the equipoise that provides the rationale for this research. Given the usual cardiopulmonary bypass time for HCM surgery

of 60 minutes a 3 minute prolongation of this time is clinically not significant. Therefore we believe that the OPIE procedure poses no clinical risk for the patients. However, we will monitor for risk by the procedures specified below. The device is small and is used under direct visualization without the need for any pressure against tissue, so there is no risk of perforation. The device is a sterile single-use object and therefore would have no additional risk of infection. The interior of the left ventricle, where the device would be used is full of blood and therefore there could not be any bleeding risk.

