### **Data Safety Monitoring Plan**

[name], Director of Echocardiography will be responsible for monitoring the conduct and safety of the study. [name] is Associate Professor, Department of Medicine and Clinical Director, Non-Invasive Cardiology.

[name] will review the chart and clinical course of the patients to confirm safety of the performance of the protocol. He will review safety after every other case. All complications will be noted and he will evaluate whether there is relation to the OPIE: mortality, infection, cerebrovascular events. Complications will be determined to be either definitely related, possibly related, or definitely unrelated.

If there is a definite or possible relation of a complication to the OPIE, the adverse event will be reported to the IRB within a week of the operation.

If there is an adverse event that is deemed definitely related to the OPIE the study will be stopped pending comprehensive review.

Reports from [name] will be forwarded to the IRB after 6 cases and after 10 cases.

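### Participation ends with the surgical hospitalisation and no safety window is defined, so deaths, infections and cerebrovascular events after discharge may go uncaptured

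*Combined protocol and SAP*

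**What the plan says.** Section 4 (Methods and Procedures) sets the end of each subject's involvement: "Subject participation will be complete after their hospitalization for surgery". It adds: "No follow-up visits are necessary, outside of the routine post-op care". Nothing is said about collecting study data from that routine care.

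The Data Safety Monitoring Plan, placed under section 10, gives one monitor the safety task. He "will review the chart and clinical course of the patients to confirm safety of the performance of the protocol". On the harms it states: "All complications will be noted and he will evaluate whether there is relation to the OPIE: mortality, infection, cerebrovascular events". On timing it states: "He will review safety after every other case". Where a complication is definitely or possibly related to the probe, "the adverse event will be reported to the IRB within a week of the operation". One definitely related event stops the study pending review. The monitor's reports go to the IRB after 6 and after 10 cases.

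Section 7 (Potential Risks) argues in advance that the probe carries no clinical risk, including: "The device is a sterile single-use object and therefore would have no additional risk of infection". It then says that risk will nevertheless be monitored by the procedures that follow.

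**The concern.** None of the three named harms is confined to the hospital stay. A patient can die, have a stroke or develop an infection after going home. The plan closes participation at the end of the hospitalisation and does not say how, or until when, such events would be found.

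Three things are at stake. First, the error has one direction: an event that is not captured can only make the safety record look better. Second, the stopping rule acts on a single definitely related event, so one uncaptured event is enough to defeat it. Third, the monitoring plan is the protocol's own check on its prior statements of no risk for an off-label use, and section 1 names safety among the things to be assessed. Without a defined window, that check is complete at most for the hospital stay.

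**Working it through.** **What the provisions give when set side by side**

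- End of participation (section 4): end of the surgical hospitalisation. No length of stay is given.
- Source of safety data (monitoring plan): chart and clinical course. No start or end of the period is given.
- Review timing: after every other case, so after cases 2, 4, 6, 8 and 10, with no minimum time since surgery. The latest patient at each review, and at the 6-case and 10-case reports, may have had very little follow-up.
- Reporting deadline: one week, counted from the operation. A related event that first appears on day 8 or later cannot meet it. The rule as written makes no provision for late events.
- Planned analysis (Sample size and data analysis): thickness differences only. There is no safety estimate, comparator or acceptance criterion.

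The plan therefore neither excludes events after discharge nor provides for finding them.

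**Illustration of size (all rates assumed)**

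The documents give n = 10 with no derivation, no event rate and no split of events by discharge, so there is no stated figure to reproduce. Let p be the assumed risk per patient of any listed event, and s the assumed share of events that occur after discharge.

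- Chance of seeing at least one event with full capture: 1 − (1 − p)^10
- The same chance if only in-hospital events are captured: 1 − (1 − p(1 − s))^10
- Expected uncaptured events in that case: 10 × p × s

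For p = 5%, s = 50%: 1 − 0.95^10 = 0.401; 1 − 0.975^10 = 0.224; 10 × 0.05 × 0.5 = 0.25.

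| p | Full capture | s = 25% | s = 50% | s = 75% | Expected uncaptured, s = 25% to 75% |
|---|---|---|---|---|---|
| 1% | 9.6% | 7.3% | 4.9% | 2.5% | 0.025 to 0.075 |
| 2% | 18.3% | 14.0% | 9.6% | 4.9% | 0.05 to 0.15 |
| 5% | 40.1% | 31.8% | 22.4% | 11.8% | 0.125 to 0.375 |
| 10% | 65.1% | 54.1% | 40.1% | 22.4% | 0.25 to 0.75 |
| 15% | 80.3% | 69.7% | 54.1% | 31.8% | 0.375 to 1.125 |

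These figures are an outer case in two ways. They assume that nothing after discharge is found, and they count every listed event, whereas the stopping rule concerns only those definitely related to the probe.

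**How much a complete window could show**

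With 0 events in 10 patients, the exact upper limit for the true rate is 1 − 0.05^(1/10) = 25.9% (one-sided 95%), or 1 − 0.025^(1/10) = 30.8% (two-sided 95%). Ten patients give weak safety evidence whatever the follow-up.

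**The case against.** A reader might infer that events after discharge are missed, that a readmitted patient would be counted as event-free, and that the trial's safety conclusion is therefore too favourable. The documents do not support this stronger reading:

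- Ending participation is not the same as ending chart review. The monitor's review has no stated cut-off at discharge, routine care continues, and section 8 says that most data come from the medical chart and that the subjects are under the care of the investigators. Earlier patients may be some way past discharge when the 6-case and 10-case reports are written.
- There is no formal safety conclusion to bias. The analysis section covers thickness only, and the section 7 statements are reasoning made before any data.
- The magnitudes rest wholly on assumed rates. The documents give no reason to expect probe-related events to be late.
- Imprecision with 10 patients limits any safety statement more than the length of follow-up does.

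All of this stands, and it limits the point to events that may be missed. It does not remove the point. A chart review with no defined end finds late events only by chance, and the deadline counted from the operation does not fit an event after the first week. With so few patients, each obtainable event matters more.

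It is also fair to object that simply lengthening the window would conflict with the one-week deadline and could hold up the reviews after every other case. The change below has to deal with both.

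**Conclusion.** The concern holds in limited form. The plan defines no observation window and no ascertainment after discharge for the harms it sets out to monitor, and its reporting deadline cannot accommodate late events. Events after discharge may go uncaptured, any under-capture is in the favourable direction, and the stopping rule may not be triggered by a late related event. As written, a safety statement can reliably cover only the in-hospital period.

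The size is unknown. Over the assumed ranges, expected uncaptured events among 10 patients run from 0.025 to about 1.1. With half of events late and p from 2% to 10%, the chance of seeing any event falls by about 38% to 48% in relative terms (for example, 1 − 22.4/40.1 = 44% at p = 5%). This rests on assumed rates and on no late event being found. The primary outcome is measured in the operating room and is not affected.

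**What to change.** In section 4 and the Data Safety Monitoring Plan:

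1. State a fixed safety window after surgery, ascertained by chart review of routine post-operative care and including readmissions. Thirty days is an example; the documents do not determine the length.
2. Keep the reviews after every other case on schedule, using the data then available, and update each case when its window closes.
3. Make the 10-case report final only after the last patient's window has closed.
4. Count the IRB reporting time from awareness of the event instead of from the operation.
5. Align the consent and authorisation wording if needed. The consent form is not in the documents reviewed, so whether it needs a change cannot be judged here.

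The cost is protocol wording, one extra chart look-up for each of 10 patients and, with a 30-day window, a final safety report about a month later. No visit, procedure or patient is added, and interim reviews are not delayed.

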#### **Sample size and data analysis:**

Each of the 10 patients will have 4 measurements(OPIE & TEE before cardiopulmonary bypass and OPIE & TEE after cardiopulmonary bypass) in the septum using two techniques (TEE and OPIE Ultrasound Probe). Primary outcome is the the difference between TEE measured septal thickness and the OPIE measured thickness before and after cardiopulmonary bypass. Center tendency parameters(mean, standard deviation) will be reported for each outcome. For example: we will report the mean and standard deviation for the difference between TEE measured septal thickness and OPIE measured thickness before and after cardiopulmonary bypass. The OPIE and TEE measurements will be compared both before and after cardiopulmonary bypass for each of the outcome as well. Accurate myectomy residual thickness is vital for success of this operation. The clinical utility of the OPIE probe will be shown if there is a  $\geq 2$ mm difference (either greater than or less than) between any single OPIE measurement and the TEE measurement either before cardiopulmonary bypass or after cardiopulmonary bypass. Given the critical nature of the assessment of septal thickness, even a 2-4 mm difference in just one patient (10% of patients) is deemed essential information.

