## **1. STUDY DESIGN**

In this pilot study we will use an ultrasound probe that is currently clinically used to assess pituitary anatomy, the Hitachi-Aloka high resolution pituitary transducer to measure left ventricular (LV) septal thickness during cardiopulmonary bypass in the performance of surgical septal myectomy. We will assess if septal thickness can be visualized during the procedure and if it is likely to improve the efficacy and safety of the procedure. The probe has FDA clearance for a variety of intra-operative surgical procedures but will be off-label for this cardiac surgical protocol. Attached is a memo from the manufacturer stating the device does not meet criteria of a “significant risk device” as per 21 CFR 812.3(m).

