## **2. OBJECTIVES**

The objective of this research project is to assess the utility an ultrasound probe that is currently clinically used to assess pituitary anatomy, the Hitachi-Aloka high resolution pituitary transducer to measure left ventricular (LV) septal thickness during cardiopulmonary bypass in the performance of surgical septal myectomy.

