## **3. RATIONALE**

There is currently no way to monitor the depth of surgical septal myectomy during the on-pump period in the OR. This is because the heart is empty of blood and transesophageal echocardiography (TEE) imaging is impossible. Also epicardial imaging is impossible. The brochure (attached separately) shows the probe we believe will let us image the septum. It may make the surgical procedure more accurate and decrease complications of “too little myectomy” or “too much myectomy”. Both can decrease the need for reoperation which is currently a risk of myectomy 1-2%. The probe is a sterile one-time-use device. The transducer itself is 2.9 mm in diameter. We have tested the probe in a simulation similar to that we will encounter during Hypertrophic Cardiomyopathy (HCM) surgery and there was excellent visualization of muscular thickness with 1:1 correlation with conventionally measured muscular wall and the ultrasound visualized thickness.

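### Each primary OPIE–TEE difference appears to compare an on-bypass OPIE reading with an off-bypass TEE reading, so a difference of 2 mm or more cannot be credited to the probe

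*Combined protocol and SAP*

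**What the plan says.** Under *Sample size and data analysis*, each of 10 patients has four septal readings, listed as "OPIE & TEE before cardiopulmonary bypass and OPIE & TEE after cardiopulmonary bypass". The primary outcome is the OPIE–TEE difference at each time point. The section continues: "The clinical utility of the OPIE probe will be shown if there is a" difference of at least 2 mm, in either direction, "between any single OPIE measurement and the TEE measurement either before cardiopulmonary bypass or after cardiopulmonary bypass". One patient in 10 is enough.

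Other sections bear on when each reading is taken:

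- Sections 1 (Study Design) and 2 (Objectives) give the probe's task as "to measure left ventricular (LV) septal thickness during cardiopulmonary bypass".
- Section 3 (Rationale) explains why the septum cannot be monitored on pump at present: "This is because the heart is empty of blood and transesophageal echocardiography (TEE) imaging is impossible".
- Section 4 (Methods and Procedures) times the first TEE: "Before cardiopulmonary bypass the anterior septal thickness at the point of mitral-septal contact will be measured by TEE in 120 degree view". The sentence on the first OPIE begins "With OPIE the PI will measure this thickness at the" and goes on to the contact lesion. It gives a site but no time. After resection there is a second OPIE and a TEE, and only the TEE is described as post-bypass.
- Sections 4 and 7 (Potential Risks) expect OPIE to add 3 minutes to bypass. Section 6 (Potential Benefits) gives the aim as monitoring while on pump.

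**The concern.** The analysis section's labels put both techniques on the same side of bypass within each pair. The rest of the protocol does not. If OPIE is read on bypass and TEE off it, every primary difference contains the measurement difference between techniques plus any real change in wall thickness between the two heart states. It also contains any effect of TEE phase or view: no cardiac phase is stated, and the 120 degree view is specified only for the pre-bypass TEE.

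The decision rule makes this matter. It does not count every shift, only a total difference of 2 mm or more in at least one pair. But a shift can help a pair reach that threshold, and when the rule is met the data cannot say whether the probe or the heart state produced the difference. The plan would still conclude that utility had been shown.

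**Working it through.** **Timing, passage against passage**

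| Reading | Label in the analysis section | Timing elsewhere |
|---|---|---|
| First TEE | before bypass | before bypass (section 4) |
| First OPIE | before bypass | not stated; on bypass by inference from sections 1, 2, 4, 6 and 7 |
| Second OPIE | after bypass | after resection (section 4); on bypass by the same inference |
| Second TEE | after bypass | after bypass (section 4) |

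The TEE labels fit and the OPIE labels do not. Section 3 rules out moving TEE onto bypass, so both pairs cross heart states.

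Sections 3 and 7 also disagree on the ventricle. Section 3 has the heart empty of blood on pump. Section 7, arguing about bleeding risk, has the ventricle full of blood where the probe is used. This does not alter the timing, but it leaves the heart state at the OPIE reading undefined.

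**The plan's own figures.** 1/10 = 10%, as stated. 10 patients × 4 readings = 40 readings, or 20 pairs. No SD, expected difference, alpha or power is given.

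**How far a shift could move the rule.** The shift and SD below are assumptions. Take each difference as Normal(m, SD), with m the heart-state shift in mm:

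- Chance that one pair qualifies: p(m) = P(|N(m, SD)| ≥ 2).
- A patient's two pairs independent: P(rule met) = 1 − [(1 − p(m1))(1 − p(m2))]^10.
- A patient's two pairs fully correlated: P(rule met) = 1 − [P(m1 + e and m2 + e both within ±2)]^10, with one e ~ N(0, SD) per patient.

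Worked case, SD 0.75 mm:

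- No shift: p = 0.0077. Correlated, 1 − (1 − p)^10 = 0.074; independent, 1 − (1 − p)^20 = 0.143.
- 1 mm at both time points: p = 0.0912. Correlated, 1 − 0.9088^10 = 0.616; independent, 1 − 0.9088^20 = 0.852.

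Chance that at least one of the 20 pairs differs by 2 mm or more (fully correlated to independent; shifts at both time points are in the same direction):

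| SD (mm) | No shift | 0.5 mm at both | 1 mm at one time point | 1 mm at both |
|---|---|---|---|---|
| 0.5 | 0.06–0.13% | 1.3–2.7% | 20.6% | 20.6–36.9% |
| 0.75 | 7.4–14.3% | 20.9–37.4% | 63.2–64.4% | 61.6–85.2% |
| 1.0 | 37.2–60.6% | 53.2–78.1% | 86.5–89.0% | 82.5–96.9% |
| 1.5 | 86.7–98.2% | 90.1–99.0% | 98.5–99.5% | 96.0–99.8% |

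Simulation of the no-shift and 1 mm cases (400,000 trials each) agreed within 0.2 percentage points. With an intermediate within-patient correlation of 0.5, a 1 mm shift at both time points takes the chance from 13.9% to 81.1% at SD 0.75 mm.

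**The case against.** The strongest reply has four parts.

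*The labels are shorthand.* Section 4 describes the same four readings, one OPIE and one TEE on each side of resection, so nobody would pair the wrong ones. That is fair, and the labels may well mean pre- and post-resection. Relabelling alone still leaves an on-bypass reading set against an off-bypass one.

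*No shift is documented.* This is also true. No passage says that septal thickness differs between the two states, and the probabilities show only what would follow if it did. Opposite-direction shifts and negative within-patient correlation are not covered. But the plan neither excludes nor measures a shift. The simulation in section 3 compared the probe with conventional wall measurement, not with TEE in patients, so it does not settle the matter.

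*The aim may be pragmatic.* OPIE could be called useful if it gives the surgeon a materially different number from TEE, whatever the cause. On that view heart state is part of the information. This is a coherent estimand, but the plan does not state it.

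*Replacing the utility rule belongs to another defect.* At SD 1 mm or more the rule is often met with no shift at all. That is a separate weakness of the rule and a further reason to change it. It does not remove this one, because a met rule would still be attributed to the probe.

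It also stands that the confounding cannot be designed out while TEE is impossible on pump. That is a reason to limit the claim.

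**Conclusion.** The concern holds. Read together, the sections put OPIE on bypass and TEE off it in both pairs. This is an inference for the first OPIE, whose time is not given. Each primary difference therefore mixes technique with heart state, and a difference of 2 mm or more cannot support the stated conclusion about the probe.

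The size is conditional on the assumed shift and SD. The effect of a shift is largest at SD below about 1 mm. A 1 mm shift at both time points adds 21 to 37 percentage points at SD 0.5 mm, 54 to 71 at 0.75 mm, 36 to 45 at 1 mm, and only 2 to 9 at 1.5 mm, where the rule is nearly always met anyway. A 0.5 mm shift at SD 0.5 mm leaves the chance below 3%. The problem of attribution does not depend on these figures.

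**What to change.** 1. In the analysis section, relabel the pairs as pre-resection (TEE before bypass, OPIE on bypass before cutting) and post-resection (OPIE on bypass after resection, TEE after bypass). State the first OPIE's timing in section 4.
2. For both TEE readings, use one stated cardiac phase, the same 120 degree view and the recorded distance below the annulus.
3. Name the primary difference as on-bypass OPIE versus off-bypass TEE. Replace the utility sentence with a descriptive report: all paired differences; mean and SD separately for pre- and post-resection (10 each); and the number of patients with a difference of 2 mm or more, with its direction, not attributed to the probe alone.
4. As supporting analysis only, show each technique's pre-minus-post change beside the specimen thickness already collected, without the 2 mm rule. This removes only a shift that is equal at both time points.
5. Reconcile sections 3 and 7 on whether the ventricle is empty or full of blood when OPIE is used.

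The cost is protocol wording, one fixed TEE frame and a weaker claim: the pilot could describe differences but could not declare utility from one pair. No patients, procedures or measurements are added.

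### The primary OPIE–TEE difference is planned without limits of agreement or confidence intervals, and the comparison is unnamed; with 10 patients the unstated uncertainty is large

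*Combined protocol and SAP*

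**What the plan says.** All references are to the combined protocol and SAP.

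- **Data.** Section 4 (Methods and Procedures) states: "The differences between the OPIE and TEE measured septal thicknesses provide the primary data points for the statistical analysis". On size it states: "We will enroll 10 subjects in this pilot study". Under Sample size and data analysis: "Each of the 10 patients will have 4 measurements(OPIE & TEE before cardiopulmonary bypass and OPIE & TEE after cardiopulmonary bypass". That makes two OPIE/TEE pairs per patient, so 10 paired differences at each time point and 20 in all.
- **Primary outcome.** It is the "difference between TEE measured septal thickness and the OPIE measured thickness before and after cardiopulmonary bypass". Absolute values are not mentioned, so the difference is most naturally read as signed.
- **Summary.** "Center tendency parameters(mean, standard deviation) will be reported for each outcome". The example given is that "we will report the mean and standard deviation for the difference between TEE measured septal thickness and OPIE measured thickness", before and after bypass.
- **Comparison.** "The OPIE and TEE measurements will be compared both before and after cardiopulmonary bypass for each of the outcome as well". No method, significance level or confidence level is named.
- **Individual rule.** Clinical utility counts as shown by a 2 mm or larger "mm difference (either greater than or less than) between any single OPIE measurement and the TEE measurement", at either time point. The section adds that such a difference in one patient, 10% of the sample, is already important.

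Limits of agreement, confidence intervals and a difference plot appear nowhere in the document.

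**The concern.** Two methods measure the same septum in the same patient. The practical question is how far one OPIE reading may lie from TEE in one patient. The plan treats individual differences as what matters, because a single pair is enough to trigger its utility rule. Yet none of its three elements answers that question with a statement of precision:

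- The mean describes average bias, and differences of opposite sign cancel in it.
- The SD describes spread, but with no indication of how poorly 10 patients determine it.
- The unnamed comparison, if it turns out to be a comparison of means, again concerns average bias only. A null result would say nothing about individual pairs.

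The single-pair rule does look at individuals, but it is a one-event trigger. It does not estimate how widely the differences range or how certain that range is.

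At stake is what the pilot can pass on to later work. A mean and SD reported bare would look more precise than 10 patients allow.

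**Working it through.** **Inputs.** n = 10 patients and one difference per patient per time point (section 4; Sample size and data analysis). The 2 mm threshold comes from the same section. The SD of the difference is not given, so results are first expressed in SD units and then illustrated for assumed SDs of 0.5 to 3 mm. Differences are taken as normal.

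**The plan's own figures.** One patient in ten is 1/10 = 10%, as stated. The sample size of 10 cannot be reproduced, because no SD, precision target, alpha or power is given.

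**Precision at n = 10**, with t(0.975, 9) = 2.262:

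1. Mean: half-width t × SD/√n = 2.262/√10 = 0.715, so ±0.72 SD.
2. SD: factors √(9/χ²) at the 97.5% and 2.5% points of χ² on 9 degrees of freedom = 0.688 and 1.826, so 0.69 to 1.83 times the estimate.
3. Limits of agreement: mean ± 1.96 SD.
4. CI of each limit, approximate: half-width t × SD × √(1/n + 1.96²/(2(n−1))) = 2.262 × √(0.1 + 0.2134) = 1.266 SD. The outer bound is 1.96 + 1.266 = 3.226 SD from the mean.
5. CI of each limit, exact: non-central t on 9 degrees of freedom, non-centrality 1.96√10, quantiles divided by √10 = 1.163 and 3.801. The upper limit therefore has a 95% CI of 1.16 to 3.80 SD above the mean.

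**Illustration with an observed mean difference of zero (mm):**

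| Observed SD (assumed) | CI of mean | Limits | Outer bound, approximate | Outer bound, exact |
|---|---|---|---|---|
| 0.5 | ±0.36 | ±0.98 | 1.61 | 1.90 |
| 1.0 | ±0.72 | ±1.96 | 3.23 | 3.80 |
| 2.0 | ±1.43 | ±3.92 | 6.45 | 7.60 |
| 3.0 | ±2.15 | ±5.88 | 9.68 | 11.40 |

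**Largest observed SD compatible with 2 mm, zero mean difference:**

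- Point limits inside ±2 mm: 2/1.96 = 1.02 mm.
- Outer bounds inside ±2 mm: 2/3.226 = 0.62 mm (approximate) or 2/3.801 = 0.53 mm (exact).

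In simulation with zero true bias, both approximate outer bounds fell within 2 mm in 79% of trials at a true SD of 0.5 mm, 49% at 0.6, 18% at 0.75 and 3% at 1.0.

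**What the single-pair rule conveys.** With zero bias and all 20 pairs treated as independent (a simplification, since each patient supplies two), the chance that at least one pair reaches 2 mm is 1 − (1 − p)^20, where p is the chance for one pair. At SD 0.75, p = 0.0077 gives 14%. At SD 1.0, p = 0.0455 gives 61%. At SD 1.5, p = 0.1824 gives 98%. Whether the rule fires thus says little about the width of the distribution.

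**Exact 95% CI for the proportion of patients at or beyond 2 mm:** 0/10 gives 0 to 31%; 1/10 gives 0.3% to 45%.

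**The case against.** The strongest case on the other side has four parts.

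- **The plan does look at individual pairs.** A reader might infer that the signed mean can hide disagreement. Five patients at +3 mm and five at −3 mm give mean 0 and SD √(10 × 9/9) = 3.16 mm, and a comparison of means would find nothing. But the 2 mm rule works in either direction and would flag all 10 patients, and the reported SD would show the spread. The plan as written would not conceal that pattern. This part stands.
- **The information is not lost.** A reader might infer that the trial cannot say how well the methods agree. In fact mean, SD and n suffice to derive the limits and every interval above, and a small enough SD would put the bounds inside 2 mm. The gap is that none of this is prespecified. The imprecision itself comes from n = 10, which the fix leaves unchanged.
- **2 mm is not an agreement margin.** A reader might take it as one. The text makes it a trigger for utility, so disagreement counts as success, and no section declares an aim of agreement within 2 mm. This stands and shapes the fix.
- **This is a pilot, and the harm is conjectural.** Section 4 calls results preliminary, no test is stated, and nothing says that a mean near zero will be read as agreement. Nor does the 3.80 mm bound mean that such differences are routine: it is a confidence bound on an extreme percentile. At SD 1.0 mm with zero bias, about 4.6% of differences exceed 2 mm. Even at the upper confidence bound for that SD (1.83 mm) it is about 27%. Descriptive reporting is not wrong in a pilot, but limits of agreement with intervals are descriptive too.

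What remains is that the range of individual differences, and its uncertainty, are not part of the planned analysis, and that the comparison has no method.

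**Conclusion.** The point holds as a reporting and precision gap. The mean and SD, the unnamed comparison and the single-pair rule together do not estimate the range of individual OPIE–TEE differences with its uncertainty. At n = 10 that uncertainty is too large to leave out: ±0.72 SD for the mean, 0.69 to 1.83 times the estimate for the SD, and 1.16 to 3.80 SD for the upper limit of agreement. An observed SD of 1.0 mm with no bias would give limits just inside 2 mm and an outer bound of 3.80 mm. The outer bound falls within 2 mm only at an observed SD of about 0.53 mm (exact) or 0.62 mm (approximate) or less.

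These figures assume normal differences and one difference per patient per time point. The millimetre values also rest on assumed SDs and a mean difference of zero. The documents do not support the stronger conclusions that the plan ignores individual pairs, that agreement could not be derived from its results, or that it declares 2 mm as an agreement margin. This is a cheap improvement and does not make the design invalid.

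**What to change.** In Sample size and data analysis, replace the sentence on mean and SD and the sentence saying that the measurements will be compared. For each time point separately, with one difference per patient, prespecify:

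1. the mean OPIE − TEE difference with its 95% CI;
2. the SD of the difference with its 95% CI;
3. the 95% limits of agreement with 95% CIs, naming the method (exact preferred at this size);
4. a plot of difference against average showing every patient, with ±2 mm drawn as reference lines only;
5. the number of patients with an absolute difference of 2 mm or more, with an exact 95% CI.

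State that a non-significant mean difference is not evidence of agreement. If a formal comparison is still wanted, name it and say that it addresses average bias.

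The sponsor should also state whether agreement or disagreement between the methods is the target. The present rule counts a difference of 2 mm or more as success, so limits inside 2 mm would look favourable on one reading and count against utility on the other.

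The cost is a few sentences and minutes of analysis, with no new data or patients. The reported precision will look somewhat less favourable than a bare mean and SD.
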